2.2 Specific Objectives

The specific objectives of the study will be:

a) develop a prototype application aimed at treating patients with SAH, including tools to improve medication adherence, monitor blood pressure values, monitor and promote physical activity and healthy lifestyle habits;

b) test the effectiveness of this application on laboratory systolic and diastolic blood pressure, adherence to drug treatment, habitual physical activity and lifestyle in hypertensive adults.

c) test the usability of this application on hypertensive adults.

3 Materials and methods

The study will be developed in three stages, according to the objectives outlined. Initially, a prototype of a cellphone application will be developed to help Brazilian adults diagnosed with SAH, with tools related mainly to medication adherence, promotion of physical activity and monitoring of blood pressure values, in addition to health tips (food, smoking, alcoholism and stress management). Subsequently, this prototype will be made available to a group of adult hypertensive patients so that the effectiveness of this application can be tested on laboratory blood pressure values, medication adherence and lifestyle aspects, including physical activity and, subsequently, physical activity. Application usability will be tested. Subsequently, after making the necessary adjustments, the application will be made available on the Apple iTunes and Google Play platforms and disseminated in groups of Basic Health Units and in the media (advertisements on television, newspaper, radio). From there, the number of downloads and the grade assigned to user reviews (one, two, three or

four stars) will be evaluated, according to the user's sociodemographic characteristics (gender, age, place of residence).

App Development

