3.2 Effectiveness testing

3.2.1 Participants

This stage of the study will involve the performance of a randomized and controlled clinical trial that will be conducted at the Sports Center of the Federal University of Santa Catarina, Florianópolis, SC. Based on a previous behavior change study¹⁹, taking systolic blood pressure as a reference, taking into account an effect size of 0.8, power of 80% and alpha error of 0.05, the estimated sample size is 52 participants (26 per group). The recruitment of these participants will be based on the dissemination of the research in the local media (radio, newspapers, internet) and in social groups, distribution of pamphlets and posting of posters in the vicinity of the evaluation sites.

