3.2.9 Assessment of habitual physical activity

Habitual physical activity will be assessed using accelerometry, using devices of the GT3X and GT3X+ models (Actigraph Pensacola, FL, USA) and the Actilife software (Actigraph Pensacola, FL, USA). Each participant will be instructed to use the accelerometer for seven consecutive days, removing it only to sleep, shower or perform water activities. The device will be placed on an elastic belt and fixed on the right side of the hip. Data will be collected at a frequency of 30 Hz and analyzed in 60 s epochs. Periods with consecutive zeros for 60 min or more (with a 2 min tolerance) will be interpreted as non-use time

and excluded from the analysis ²¹. For analysis purposes, a minimum of 10 hours of daily activity recordings, for at least four days, three weekdays and one weekend day will be considered valid data. The average time spent in each intensity of physical activity will be calculated from the cut-off points proposed by Freedson et al. ²², considering sedentary behavior as 0 – 99 counts/min, light physical activities as 100-1951 counts/min, moderate physical activities as ≥ 1952 counts/min and vigorous or very vigorous activities as ≥ 5725 counts/min. Data will be analyzed in min/day, adjusted by number of days of use and daily time of use.

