3.2.12 Statistical analysis plan (SAP)

Initially, the normality and homogeneity of variance will be analyzed using the Shapiro-Wilk and Levene tests, respectively. For data that do not have a normal distribution, logarithmic transformation will be performed. Student 's t test for independent samples and the chi-square test will be used to compare the groups at the pre-intervention moment, regarding continuous and categorical variables, respectively.

For the Intra and inter-group comparisons of quantitative and qualitative variables, the method of generalized estimation equations will be used (group: GA and GC; time: pre and post-intervention assessments; interaction (group vs. time), after confirming the appropriate assumptions. In all analyses, when a significant effect is verified, the Newman-Keuls post-hoc test will be used, with a P value <0.05 being considered significant.

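### No primary outcome is named and each effectiveness outcome is tested at P<0.05 with no control across outcomes, so an overall claim that the app works is not held to a 5% error rate

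*Combined protocol and SAP*

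**What the plan says.** - **Objectives (2.2, item b).** The trial is to "test the effectiveness of this application on laboratory systolic and diastolic blood pressure, adherence to drug treatment, habitual physical activity and lifestyle". That is five headings, with no order among them.
- **Sample size (3.2.1).** The calculation is made "taking systolic blood pressure as a reference", "taking into account an effect size of 0.8, power of 80% and alpha error of 0.05", and gives 52 participants, 26 per group. SBP is not called the primary outcome here or elsewhere.
- **Physical activity (3.2.9).** "The average time spent in each intensity of physical activity will be calculated", using cut-offs for four bands: sedentary, light, moderate, and vigorous or above. The section does not say which of these is the outcome.
- **Lifestyle (3.2.10).** The questionnaire has five components. The section does not say whether a total or each component is analysed.
- **Analysis (3.2.12).** Generalized estimating equations with group, time and group-by-time terms are applied to the quantitative and qualitative variables. Then: "In all analyses, when a significant effect is verified, the Newman-Keuls post-hoc test will be used, with a P value <0.05 being considered significant". No adjustment across outcomes is given, and no term of the model is named as the one that decides.

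**The concern.** The type I error of 5% and power of 80% in 3.2.1 describe one comparison on one outcome. The analysis section tests at least five outcomes at that same level and does not say which of them settles whether the app is effective. Newman-Keuls does not fill this gap: it compares means within one outcome's model and does nothing across outcomes.

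Without a hierarchy, a report could present the app as effective because of a questionnaire score or one activity band while SBP shows no difference. Nothing in the plan would mark that as a departure. With 26 people per group and self-reported adherence and lifestyle, the error rate of such a claim should be known beforehand.

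**Working it through.** **Step 1: reproduce the sample size.** Inputs from 3.2.1: standardised effect d = 0.8, alpha 0.05, power 80%. The section does not state sidedness.

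- Normal approximation, two-sided: n per group = 2 × (1.960 + 0.842)² / 0.8² = 2 × 7.85 / 0.64 = 24.5, so 25.
- Two-sided t-test: 25.5, so 26 per group and 52 in total. This is the plan's figure. Power at 26 per group is 80.7%.
- One-sided t-test: 20.03, so 21 per group, which does not match.

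The stated alpha and power therefore describe a single two-sided comparison of SBP.

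**Step 2: count the outcomes.**

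- Five, if each heading in objective (b) gives one test.
- Eight, if activity is tested as four bands: SBP, DBP, adherence, four bands, lifestyle.

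The documents do not settle which count applies.

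**Step 3: chance of at least one false positive.** Assume no true effect on any outcome and one group-by-time test per outcome, each two-sided at 0.05. For k independent outcomes:

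- Either direction: 1 − 0.95^k. For k = 5: 1 − 0.774 = 22.6%. For k = 8: 1 − 0.663 = 33.7%.
- Favouring the app only: 1 − 0.975^k. For k = 5: 1 − 0.881 = 11.9%. For k = 8: 1 − 0.817 = 18.3%.

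The documents give no correlations between outcomes, so these are assumed. For correlated outcomes, normal test statistics with a common correlation r were simulated (1,000,000 draws), coded so that positive values favour the app.

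| Outcomes and direction | r = 0 | r = 0.3 | r = 0.5 | r = 0.7 |
|---|---|---|---|---|
| 5, either direction | 22.6% | 20.9% | 18.3% | 14.8% |
| 8, either direction | 33.7% | 29.9% | 25.0% | 19.1% |
| 5, favouring the app | 11.9% | 10.5% | 9.2% | 7.4% |
| 8, favouring the app | 18.3% | 15.2% | 12.6% | 9.5% |

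The benchmark is 5% (either direction) or 2.5% (favouring the app) for a single test.

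A less uniform pattern was also tried: SBP and DBP correlated at 0.5 to 0.8, the four bands with each other at 0.3 to 0.7, and everything else independent. The either-direction rate is then 21.0-22.1% for five outcomes and 27.7-32.2% for eight.

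**Step 4: compare the remedies.** Two-sample t-test, d = 0.8, 26 per group:

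| Approach | Power | Per group for 80% power |
|---|---|---|
| SBP as single primary, 0.05 | 80.7% | 26 |
| Bonferroni over five, 0.01 | 58% | 39 |
| Bonferroni over eight, 0.00625 | 52% | 42 |

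**The case against.** The strongest reply is that the plan contains no rule under which any one significant outcome proves the app effective. Section 3.2.12 says only when a P value is called significant. Objective (b) can be read as five outcome-specific questions, each answered at its own 5% level. SBP is the only outcome used for sizing, and randomization takes account of pre-intervention blood pressure (3.2.3), so SBP is the natural candidate for primary. On that reading the SBP test has exactly the error rate assumed in 3.2.1, and the other tests do not alter it.

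Much of this stands. The gap is an omission, not a stated any-one-wins rule. A reader might also infer that the alpha behind the sample size is broken. It is not: 52 is reproduced, and the SBP comparison keeps its nominal 5%. The reply does not supply what is missing, though. No section says that SBP decides, or that the five answers must not be merged into one claim of effectiveness. Section 3.4 says the trial will be registered, but that record is not part of these documents.

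A second reply is that full independence is not credible, because the activity bands divide the same wear time and SBP and DBP move together. That is fair, and is why the rates are given as ranges. Even at r = 0.7 they are about three to four times the benchmark (14.8/5 = 3.0 and 19.1/5 = 3.8). The calculation may also understate the risk: it allows one test per outcome, whereas 3.2.12 includes group, time and interaction effects and within-group comparisons.

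**Conclusion.** The point holds as a missing designation with a calculable consequence. No outcome is primary, each is tested at P<0.05, and nothing controls error across them. If any significant outcome may support an effectiveness claim, then with correlations of 0.5 down to 0 the chance of at least one false positive in either direction is about 18-23% for five outcomes, or 25-34% for eight. False results favouring the app account for about 9-12% and 13-18%, roughly four to seven times the 2.5% of a single test.

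Two stronger readings are not supported:

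- **That a false claim that the app works has a 25-34% chance.** That range needs eight outcomes and an assumed correlation, and it counts differences against the app as well as for it.
- **That the risk reaches 46%** (1 − 0.95^12). That needs the five lifestyle components tested separately, alongside four activity bands, with all 12 outcomes independent. Section 3.2.10 does not plan separate component tests.

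The omission is certain from the text. The percentages depend on the stated assumptions about outcome count, correlation and how the results would be used.

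**What to change.** In 3.2.12:

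1. Name the SBP group-by-time comparison at week 8, two-sided 0.05, as the single primary test, and state that effectiveness is claimed only on it.
2. Make DBP, adherence, one prespecified activity measure and one prespecified lifestyle score secondary. Report Holm-adjusted P values (with four outcomes, the smallest is compared with 0.05/4 = 0.0125), or estimates with 95% confidence intervals only. The activity measure and lifestyle score must be chosen and defined, since 3.2.9 and 3.2.10 do not single one out.
3. Label the remaining activity bands and lifestyle components exploratory.

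This costs some wording and a few adjusted P values; the sample size stays at 52. The real price is that a significant secondary result can no longer carry the effectiveness claim alone. Keeping all outcomes co-equal under Bonferroni would cost far more, in power or in participants.

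One caution: the 80.7% power is for a two-sample t-test at d = 0.8 with 26 per group. It carries over to the group-by-time test only if d = 0.8 refers to that contrast and nobody drops out. Section 3.2.1 states neither, so the amended text should say which contrast the effect size describes.

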3.3 Usability and patient satisfaction testing

After the application is made available on Apple iTunes and Google Play and the application is disseminated in groups of Basic Health Units and in the media (advertisements on television, newspaper, radio), the number of downloads and the grade assigned to user evaluations will be evaluated (one, two, three or four stars), according to the sociodemographic characteristics of the user (gender, age, place of residence).

3.4 Ethical issues

This study will be submitted to the Research Ethics Committee of the Federal University of Santa Catarina, will follow the rules of Resolution 466/12 of the National Health Council on research involving human beings and the stage involving the performance of the clinical trial will be registered at ClinicalTrials.gov.
